9.5.2 Co-Primary Efficacy Analysis

Results of the co-primary endpoint Change from Baseline in Corneal Staining at Week 8 will be summarized descriptively by treatment group for Main Eye and Secondary Eye for the FAS.

For the co-primary analysis LOCF is applied as described in section 7.2.7. The exploratory p-value and estimates for treatment effect as well as treatment group difference resulting from the ANCOVA analysis specified in section 8.2 will be reported in addition for the Main-Eye results at Week 8.

For supportive purposes, this analysis of Main Eye results at Week 8 will be repeated for the PPS to investigate the effect of protocol deviations on the results.

If the covariate ‘Number of Study Eyes’ would result in a significant effect, the ANCOVA analysis will be repeated for each subgroup separately.

To investigate the influence of within and between patient variability, a descriptive analysis will be presented based on subgroup of patients in the FAS with 2 study eyes including CFB in Corneal Staining in Main Eye, Secondary Eye as well as the Individual Mean Change (i.e. mean of change in Main and Secondary Eye in each patient) and Individual Difference between Study Eyes at Week 8.

A similar analysis will be performed for the absolute values as well as for CFB in Corneal Staining (without imputation) at Week 4, Week 8 and Week 12. ANCOVA analysis will be performed for CFB at Week 8 in the Main Eye. This analysis will be performed for the FAS and all data will be listed for the FAS.

9.5.3 Secondary Efficacy Analysis

The secondary endpoints Conjunctival Staining, TFBUT as well as Corneal Sensitivity endpoints (absolute values as well as CFB) will be summarized descriptively for patients in the FAS by treatment group and study visit for Main Eye and Secondary Eye. No inference will be performed for these parameters.

Listing on secondary efficacy endpoints including assessments for Main Eye and Secondary Eye will be provided for FAS, in addition.

9.6 Safety Results

9.6.1 Adverse Events

9.6.1.1 Brief Summary of Adverse Events

Reporting of AEs is focused to treatment emergent AEs.

An overview of AEs, TEAEs, TEAEs during Treatment Period, TEAEs during Follow-up Period, TEAEs leading to premature withdrawal of the study treatment. TEAEs leading to study discontinuation, serious TEAEs, Fatal TEAEs, treatment related TEAEs, treatment related serious TEAEs, TEAEs of special interest and Mild, Moderate and Severe TEAEs will be given by study treatment and overall for patients in the SAF. For each events, the number and percentages of patients with at least one event as well as the total number of events will be provided.

9.6.1.2 Display of Adverse Events

Adverse event descriptive tables will be summarized separately for each study treatment and overall.

They will be summarized on a per-patient basis (i.e. if a patient reported the same event repeatedly the event will be counted only once at the specific level of display). Absolute counts (n) and percentages (%) will be presented for the number of patients with at least one Adverse event, and per SOC and per PT within SOC, for the SAF. Percentages will be based on the number of patients in the population. In addition number of events will be provided.

Descriptive tables will be ordered by descending frequency of the overall number of patients within each SOC regardless of treatment group, and then ordered within each SOC by the overall number of patients within each PT regardless of treatment group. In the event of equal frequencies tables will be ordered by active treatment frequency and then alphabetically.

The following tables will be provided:

- Non-TEAE
- TEAEs
- TEAEs by severity.
- Treatment related TEAEs.
- Serious TEAEs.
- Treatment related serious TEAEs
- TEAEs that occur with a relative frequency in the active treatment of at least twice the relative frequency in the vehicle group.
- TEAEs leading to premature withdrawal of the Study Treatment.
- TEAEs leading to study discontinuation.
- TEAEs during Treatment Period
- TEAEs during Follow-up Period.

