3.6 Sample Size estimation

Sample size was calculated by assuming at single eye level a mean difference from baseline mean SANDE scores of -30±20 in the rhNGF groups versus -20±20 in vehicle group (80% power, alpha =0.05; 2-sided test), considering that the active comparator has already proven safe and effective in dry eye patients. The sample size has been calculated based on a 2:1 randomization by the following formula:

$$n1 = (0.5) \times n \times (1 + k)$$

$$n2 = (0.5) \times n \times (1 + (1/k))$$

with n1= active treatment and n2= vehicle and n= 63 and k= n1 /n2 = 2/1=2. Therefore n1= 94,5 and n2=47.25. Assuming a 5% drop out rate, a total of 100 patients in the active arm and 50 in the vehicle arm are required.

However, in order to provide the mean of detecting a significant difference also on a clinical sign of the effect of the rhNGF therapy (namely Co-primary Efficacy Endpoint cornea vital staining with fluorescein (National Eye Institute [NEI] scales)), sample size calculation was also performed by assuming, at single eye level, a mean difference from baseline in Cornea NEI scale scores of -3.9 ± 2.2 in the rhNGF groups versus -2.9 ± 2.2 in vehicle group (80% power, $\alpha = 0.05$; 2-sided test), considering that the active comparator has already proven safe and effective in dry eye patients. The sample size has been calculated based on a 2:1 randomization by the following formula:

$$n1 = (0.5) \times n \times (1 + k)$$

$$n2 = (0.5) \times n \times (1 + (1/k))$$

with $n1 =$ active treatment and $n2 =$ vehicle and $n = 76$ and $k = n1 / n2 = 2/1 = 2$. Therefore $n1 = 114$ and $n2 = 57$. Assuming a 5% drop out rate, a total of 120 patients in active arm and 60 in the vehicle arm are required. This calculation is based on one study eye per patient. (Whereas also two study eyes per patient may occur, that will increase power to above 80%).

Considering the two calculations performed to determine the sample size, in this study will be enrolled 180 patients (120 patients enrolled in active arm and 60 in the vehicle arm) in order to detect both changes at the same time in the variables.

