7.2.8 Safety Variables

Adverse Events (AE)

AE data are collected on the 'Adverse Events' eCRF page. Corrective medications or procedures due to an AE are documented on the eCRF pages 'Prior and Concomitant Medications' and 'Concomitant Procedures' respectively.

The AE Description (Investigator term) will be analyzed on Preferred Term (PT) and System Organ Class (SOC) level using MedDRA.

Based on the information provided on the 'Adverse Events' eCRF page, the following definitions will be utilized:

- An ocular event will be identified, if the question 'Is this an ocular event?' is answered 'Yes'.
- An AE with missing severity will be counted as severe.
- A Serious Adverse Event (SAE) is any adverse event where the question 'Is the event serious?' has been answered as 'Yes'. If this question is not answered the event will be considered as 'Serious' for analysis purposes.
- *The following adverse events are considered to be of special interest (AESI) and by default shall be reported as SAEs (medically important criteria):*
 - *AEs that caused a decrease in visual acuity of >30 ETDRS letters or > +0.6 LogMAR (compared with the last assessment of visual acuity at the last visit) lasting >1 hour*
 - *AEs that caused a decrease in visual acuity to the level of Light Perception or worse lasting >1 hour*
 - *AEs that required surgical intervention (e.g., conventional surgery, vitreous tap or biopsy with intravitreal injection of anti-infectives, or laser or retinal cryopexy with gas) to prevent permanent loss of sight*
 - *AEs associated with severe intraocular inflammation (i.e., 4+ anterior chamber cell/flare or 4+ vitritis)*
 - *AEs that, in the opinion of the Investigator, may require medical intervention to prevent permanent loss of sight.*

For analysis purposes, AESI will be identified by ticked box 'Medically significant or important medical condition' in the eCRF section 'SAE criteria'. This means in particular, that all AESIs will be considered as SAEs.

- An AE leading to premature withdrawal of the study treatment is defined as an AE where in the eCRF section 'Action taken with study treatment' the boxes 'Withdrawn' and 'Definitely' are ticked.
- An AE leading to study treatment interruption is defined as an AE where in the eCRF section 'Action taken with study treatment' the boxes 'Withdrawn' and 'Temporarily' are ticked.

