- An AE leading to study discontinuation is defined as an AE where in the eCRF section 'Action regarding Patient' the box 'Patient Withdrawn' is ticked (this should match with the primary reason for early withdrawal of 'Adverse Event' on the End of Study eCRF page).
- An AE is classified as 'Related' to Study Treatment if the relationship to study medication recorded as 'Possible' or 'Probable' or 'Highly Probably'. An AE will be classified as unrelated to study medication if the relationship to study medication was recorded as 'None' or 'Unlikely'. AEs with missing relationship to study treatment will be counted as 'Related' to Study Treatment.
- A Fatal AE is defined as an AE where the outcome is recorded as 'Fatal'.

These definitions will apply accordingly also for the subsequent sub-classes of AEs.

Non Treatment-emergent adverse events (Non-TEAEs)

A Non-TEAE is defined as any AE, which started before the first administration of study treatment. They are identified by the ticked box 'Before Treatment Period' in the eCRF Section 'Did the event occurred:'.

Treatment-emergent adverse events (TEAEs)

A treatment-emergent adverse event is defined as an AE that started on or after the date of the First Study Treatment Administration. A TEAE will be identified, if The eCRF question 'Did the event occurred:' was answered either with 'During Treatment period' or 'During Follow-Up Period'.

The incidence and frequency of TEAEs will serve as safety endpoint of the study.

TEAEs in the Treatment Period

This will be defined as a TEAE (as defined above) with a start date on or after the date of first study treatment administration and before the Week 8 Visit. It will be identified, if eCRF question 'Did the event occurred:' was answered with 'During Treatment period'.

TEAEs in the Follow-up Period

This is defined as a TEAE (as defined above) with a start date on or after the Week 8 Visit. It will be identified, if eCRF question 'Did the event occurred:' was answered with 'During Follow-Up period'.

For listing purposes, treatment day of onset of AE will be presented according to the definition given in section 7.1.

Missing Codes or Incomplete AE start dates:

In the event that coding information will not be available for a specific AE, the event will be presented as 'Uncodable Event'). However, for final TLFs it is anticipated that all events are coded.

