Table 14.2-3.2	Summary of Change from Baseline of Corneal Staining at Week 8 (LOCF) (FAS)
Table 14.2-3.2.1	Summary of Change from Baseline of Corneal Staining at Week 8 in Subgroups (LOCF) (FAS)
Table 14.2-3.3	Summary of Corneal Staining at Week 8 (LOCF) (PPS)
Table 14.2-3.4	Summary of Change from Baseline of Corneal Staining at Week 8 (LOCF) (PPS)
Table 14.2-3.5	Summary of Change from Baseline of Corneal Staining at Week 8 in Subgroup of Patients with 2 Study Eyes (LOCF) (FAS)
Table 14.2-4.1	Summary of Corneal Staining by Visit (Observed) (FAS)
Table 14.2-4.2	Summary of Change from Baseline of Corneal Staining (Observed) (FAS)
Table 14.2-5.1	Summary of Conjunctival Staining by Visit (FAS)
Table 14.2-5.2	Summary of Change from Baseline of Conjunctival Staining by Visit (FAS)

TLF Number	Title
Table 14.2-6.1	Summary of Other Secondary Efficacy Endpoints by Visit (FAS)
Table 14.2-6.2	Summary of Change from Baseline of Other Secondary Efficacy Endpoints by Visit (FAS)
Table 14.3.1-1.1	Summary of Exposure (SAF)
Table 14.3.2-1.1	Overall Summary of Adverse Events (SAF)
Table 14.3.2-2.1	Summary of Non-TEAEs by System Organ Class and Preferred Term (SAF)
Table 14.3.2-3.1	Summary of TEAEs by System Organ Class and Preferred Term (SAF)
Table 14.3.2-4.1	Summary of Treatment Related TEAEs by System Organ Class and Preferred Term (SAF)
Table 14.3.2-5.1	Summary of Serious TEAEs by System Organ Class and Preferred Term (SAF)
Table 14.3.2-6.1	Summary of Serious Treatment Related TEAEs by System Organ Class and Preferred Term (SAF)
Table 14.3.2-7.1	Summary of TEAEs with a Relative Frequency in the Active Treatment Group of At Least Twice the Relative Frequency in the Vehicle group by System Organ Class and Preferred Term (SAF)
Table 14.3.2-8.1	Summary of TEAEs Leading to Premature Withdrawal of the Study Treatment by System Organ Class and Preferred Term (SAF)
Table 14.3.2-9.1	Summary of TEAEs Leading to Study Discontinuation by System Organ Class and Preferred Term (SAF)
Table 14.3.2-10.1	Summary of TEAEs during Treatment Period by System Organ Class and Preferred Term (SAF)
Table 14.3.2-11.1	Summary of TEAEs during Follow-Up Period by System Organ Class and Preferred Term (SAF)
Table 14.3.2-12.1	Summary of TEAEs by Severity, System Organ Class and Preferred Term (SAF)
Table 14.3.3-1.1	Summary of BCDVA score (SAF)
Table 14.3.3-1.2	Summary of Change from Baseline of BCDVA (SAF)
Table 14.3.3-2.1	Summary of logMAR (SAF)

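### The one adverse-event table that selects terms by comparing arms uses a bare ratio of at least 2 with no minimum count or interval, and no planned table totals ocular TEAEs

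*SAP*

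**What the plan says.** SAP 9.6.1.2 names eleven adverse-event tables. All share one layout: "Adverse event descriptive tables will be summarized separately for each study treatment and overall". Counting is by patient ("if a patient reported the same event repeatedly the event will be counted only once at the specific level of display"), and "Percentages will be based on the number of patients in the population", which is the Safety Set.

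Ten of the eleven choose their events by type, severity, relationship, consequence or period. The remaining one chooses them by comparing the arms: "TEAEs that occur with a relative frequency in the active treatment of at least twice the relative frequency in the vehicle group". The list of tables in SAP section 11 repeats the rule under number 14.3.2-7.1, where the title reads "Summary of TEAEs with a Relative Frequency in the Active Treatment Group of At Least Twice the Relative Frequency in the Vehicle group", broken down to organ class and preferred term. Neither place gives a minimum count, says how 0% on vehicle is treated, or adds a difference, ratio or confidence interval. No other adverse-event table carries a between-arm statistic.

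The arm sizes come from SAP 3.6: "120 patients enrolled in active arm and 60 in the vehicle arm".

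On ocular events, SAP 7.2.8 states: "An ocular event will be identified, if the question 'Is this an ocular event?' is answered 'Yes". The overview (9.6.1.1), the table list (9.6.1.2), the specific listings (9.6.1.3) and the titles in section 11 do not mention ocular events again in connection with adverse events.

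Safety is half of the primary objective (SAP 3.1), and SAP 7.2.8 adds: "The incidence and frequency of TEAEs will serve as safety endpoint of the study".

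**The concern.** A reader who wants to know which events may be more frequent on rhNGF will go to the table that selects on exactly that. A bare ratio serves this badly at both ends of the frequency range. For rare terms, one patient on rhNGF and none on vehicle is enough, and 2:1 allocation puts most isolated events on rhNGF by design. For common terms, a ratio of 2 requires a large absolute excess, so a difference of many percentage points can stay below the line. The table shows no interval that would let the reader tell these cases apart.

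The second matter is ocular tolerability. For an eye drop, the number of patients per arm with any ocular TEAE is a basic figure. The site answers the ocular question event by event, separately from MedDRA coding. An event marked ocular but coded to another organ class is therefore not in the eye-class row. The field is collected and defined, but no planned table uses it to produce the total.

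**Working it through.** **Arm sizes, reproduced first.** The documents give no operating characteristics for the ratio rule, but they do give the arm sizes that fix its behaviour. For corneal staining (difference 1.0, SD 2.2, 80% power, two-sided 0.05), n per arm at 1:1 = 2 × (1.96 + 0.84)² × 2.2² / 1.0², which rounds up to 76. The SAP formula then gives 0.5 × 76 × 3 = 114 and 0.5 × 76 × 1.5 = 57. Dividing by 0.95 gives 120 and 60, as stated.

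**The rule in counts.** Let X and Y be the numbers of rhNGF and vehicle patients with the term. X/120 ≥ 2 × Y/60 is the same as X ≥ 4Y. A term is listed if X ≥ 1 and X ≥ 4Y. This takes the Safety Set as 120 and 60, and lets 0% on vehicle satisfy the rule, which is the literal reading.

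**No drug effect, given the number of affected patients** (hypergeometric, 120 of 180 on rhNGF):
- 1 patient: 120/180 = 66.7% listed (50% at 1:1)
- 2 patients: 44%
- 3 patients: 29%
- 4 patients: 19%

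**No drug effect, given an event rate.** The documents state no event rates, so these are assumptions. X ~ Bin(120, p) and Y ~ Bin(60, p). At p = 1%, P(Y = 0, X ≥ 1) = 0.383 and P(Y ≥ 1, X ≥ 4Y) = 0.011, total 0.394. The chance that the term occurs at all is 1 − 0.99^180 = 0.836. The conditional listing probability is 0.472 (from unrounded values). At 2% it is 0.362 and at 5% it is 0.232.

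**Real effects** (exact binomial, unconditional):

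| Vehicle | rhNGF | Listed | Missed |
|---|---|---|---|
| 1% | 2% | 57.2% | 42.8% |
| 2% | 4% | 57.9% | 42.1% |
| 5% | 10% | 55.1% | 44.9% |
| 10% | 20% | 53.6% | 46.4% |
| 15% | 30% | 52.9% | 47.1% |
| 20% | 35% | 34.9% | 65.1% |
| 5% | 15% | 80.3% | 19.7% |
| 10% | 30% | 87.9% | 12.1% |

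With 114 and 57 patients, 5% against 10% is listed 55.2% of the time.

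**Is allocation the cause of the missed doublings?** At 90 and 90 patients, 5% against 10% is listed 55.3% of the time, against 55.1% at 120 and 60. It is not the cause. A cut-off placed at the true ratio misses about half whatever the split.

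**Two observed results side by side** (Newcombe 95% interval for the risk difference):
- 1/120 against 0/60: listed. Difference 0.8 points (−5.2 to 4.6).
- 23/120 (19.2%) against 6/60 (10.0%): ratio 1.92, 24 patients needed, not listed. Difference 9.2 points (−2.6 to 18.7).

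**The replacement filter, checked in the same way.** A threshold of X ≥ 3 lists a term with equal 5% rates 94% of the time (ratio rule 23%), and a 1% to 2% doubling 43% of the time (ratio rule 57%). It lists the 5% to 10%, 10% to 20% and 20% to 35% cases practically always. With at least 2% in either arm (X ≥ 3 or Y ≥ 2), the 1% to 2% doubling is shown with probability 1 − P(X ≤ 2) × P(Y ≤ 1) = 1 − 0.569 × 0.879 = 0.50.

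**The case against.** The strongest reply is that nothing is lost from reporting. The full TEAE table gives every organ class and preferred term with n (%) per arm, so a term that fails the ratio rule is still shown side by side. That stands. A reader might infer that real differences go unreported, and the documents do not support it. The SAP also never states a purpose for the ratio table.

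Three other strong readings are tempting and should be resisted.
- That 2:1 allocation causes the missed doublings. It does not; the result at 90 and 90 is almost the same. Allocation explains only the two-thirds figure for isolated events. The 20% to 35% case has a true ratio of 1.75, so leaving it out is what the rule asks for, and triplings are usually caught.
- That chance terms will make up most of the table. The figures are listing probabilities per term. The make-up of the table depends on how many terms occur, at what rates and with what effects, and the documents give none of these.
- That the ocular flag is not used at all. SAP 9.6.1.3 plans listings of all adverse-event data, which may print it, and SAP 7.2.8 extends its definitions to the sub-classes of adverse events. The mock shells are a separate document that was not available. An eye-class total per arm will also be produced, and visual acuity, slit-lamp and external findings are tabulated by eye and arm. What remains is that no planned table title shows ocular TEAE incidence across organ classes. How many events fall outside the eye class is unknown.

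Finally, the study is declared exploratory, and inference was added only for the primary and co-primary efficacy endpoints. A safety interval is therefore a choice of display, not a requirement. The proposed filter is also not a better detector in itself: it shows common terms with no difference, and fewer of the rarest doublings. The gain comes from the risk difference and its interval.

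**Conclusion.** The point holds as a minor improvement to the safety display. The only adverse-event table with a between-arm criterion lists an isolated, drug-unrelated term two times in three, and a 1% term with no effect 47% of the time if it occurs. It omits 42% to 48% of true doublings over vehicle rates of 0.5% to 25%. It gives the reader nothing by which to judge either. The harm is limited to one misleading supplementary extract, because the full TEAE table remains. Separately, a per-patient ocular TEAE incidence that includes events coded outside the eye class is not visibly planned, although the field for it exists.

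The two-thirds figure needs only 120:60 allocation, no drug effect and the literal reading of 0% on vehicle. The other percentages rest on assumed event rates. The ocular point rests on the SAP text and table titles alone.

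**What to change.** Redefine Table 14.3.2-7.1. List preferred terms reported in at least 3 rhNGF patients (3/120 = 2.5%, the first count to reach 2%), or alternatively in at least 2% of patients in either arm. Show n (%) per arm, the risk difference and a 95% confidence interval labelled descriptive, ordered by risk difference. Keep the full TEAE table for rarer terms.

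Add ocular and non-ocular rows or by-groups, from the existing eCRF flag, to the overview, TEAE, treatment-related TEAE and TEAE-by-severity tables. If the mock shells already contain such a split, say so in SAP 9.6.1.

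The cost is one redefined table and a by-group on four others. Protocol 10.6 asks for TEAEs by organ class and term, seriousness, relationship and severity, and does not ask for the ratio table, so no protocol amendment is needed. There are two downsides. Terms seen in one or two rhNGF patients would appear only in the full table and listings (under the either-arm version, also here if at least 2 vehicle patients report them). Common terms with no difference would also be shown, with the interval as the reader's guide.

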9.6.1.3 Listings of Adverse Events

Listings will present all Adverse Event data for the SAF by patient.

In addition specific listings will be created for:

- TEAEs leading to premature withdrawal of study treatment
- TEAEs leading to study treatment interruption
- TEAEs related to study treatment
- Serious AEs
- Serious TEAEs related to study treatment
- Fatal TEAEs

Corrective procedures as documented on the eCRF page 'Concomitant Procedures' will be listed for all patients in the SAF.

9.6.2 Clinical Laboratory Evaluation

A Listing will be provided for patients in the SAF displaying the results of pregnancy tests at Baseline, Week 4 and Week 8 as documented on the eCRF Page 'Urine Pregnancy Test'.

9.6.3 Best Corrected Visual Acuity

BCDVA score and logMAR (absolute values as well as changes from baseline) will be summarized descriptively by treatment group and study visit for the Main Eye as well as the Secondary Eye. This analysis will be performed on the SAF. All BCDVA data will be listed.

